The change in QOL from baseline will be measured, using the disease-specific KCCQ score, the SF-12 general health status index, and EQ-5D measures of health state preference from the individual and societal perspective. The KCCQ is a widely used tool in heart failure populations. The SF-12 is a general health status measure. This instrument examines 8 quality of life dimensions (physical activity, social activity, role/physical, body pain, general mental health, role/emotional, vitality and general health perception). The EQ-5D is a standardized instrument for measuring health-related quality of life. This questionnaire provides a simple descriptive profile that consists of 5 dimensions. The 5 domains are anxiety/depression, pain/discomfort, usual activities, self-care, and mobility. The instrument also has a self-assessment of health status.

For this trial, the SF-12, EQ-5D, and KCCQ are available in English, Spanish, French and German. Inability to read and complete these instruments in the available languages does not preclude a patient from enrollment in the trial (a family member may assist in completing the QOL questionnaires).

Survival

Perioperative and all-cause mortality over 60 months will be assessed.

Hospitalizations

Length of Index Hospitalization

Overall length of stay (LOS) for the index hospitalization will be measured (and broken down by days spent in the ICU versus days spent on telemetry and regular floors). LOS will be measured as time from index surgery to discharge. In addition, we will capture discharge location.

Readmission and Reoperations

Readmission rates will be calculated for the first 30 days following intervention and through 24 months post-randomization. Hospitalizations will be classified for all causes, including cardiovascular and heart failure readmissions and readmissions for TR operation. Classification of a readmission as heart failure related requires *at least 2* out of the following signs and symptoms of acute decompensated heart failure:

- Dyspnea felt related to heart failure
- Treatment with intravenous diuretic, vasodilator or inotropic therapy
- X-ray evidence of pulmonary edema or pulmonary vascular congestion
- Rales on physical exam
- PCWP or LVEDP > 18 mmHg

All readmissions will be classified by the investigator and adjudicated by the EAC.

All re-operations and re-operation for TR in particular will be recorded through 24 months post-randomization. Freedom from re-operation will be analyzed.

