The inclusion and exclusion criteria will be documented by the clinical site study coordinator and verified with the site Principal Investigator in the Randomization Eligibility Form. The degree of TR will also be recorded for stratification purposes. All screened patients (patients who are consented) who are not randomized in the trial will have the reasons for non-randomization documented in the Randomization Eligibility

Form. The data collected is compliant with privacy regulations and includes reason for not being randomized.

A representative from the DCC will be available to discuss any questions regarding patient eligibility.

RANDOMIZATION

The randomization procedure will be performed intra-operatively, following the placement of the TEE probe and after visualization and confirmation of cardiac anatomy eligibility. Randomization to the study assignment will be generated by the EDC once the checklist of inclusion and exclusion criteria has been completed and verified. For the purpose of the primary analysis, patients are considered enrolled in the study once they are randomized.

PROCEDURE

Surgical Procedure

Patients will be randomized to either (a) TV repair using a legally marketed annuloplasty ring in addition to the MVS, or (b) MVS alone.

After induction of anesthesia, all patients will undergo a TEE. The TEE will be performed under loading conditions as close as possible to the patient's baseline. Intra-operative TEEs will be performed according to standardized acquisition protocol developed by the Echo Core Lab ([Appendix I](#) and [Appendix II](#)). A laminated copy of this acquisition protocol will be provided to the site and affixed to the operating room echo machine.

All procedures will be performed using cardiopulmonary bypass support and cardioplegic arrest. The management of cardiopulmonary bypass and myocardial protection will be at the discretion of the surgeon, using standard techniques. MV repair or replacement will be performed using standard techniques.

Tricuspid valve surgery

Patients randomly assigned to receive TV repair in addition to MVS will undergo concomitant TV repair.

It is recognized that surgical techniques for TV surgery may need to be adjusted at the discretion of the surgeon based on intra-operative findings that may not be previously recognized in the preoperative evaluation. The common elements for tricuspid annuloplasty planned as part of this study are listed below:

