- 6 (± 30 days), 12 (± 30 days), 18 (± 30 days) and 24 months (± 60 days) post-randomization

²Needs to be manually bent into nonplanar shape similar to other commercially available annuloplasty rings

- 36, 48 and 60 months vital status check (± 60 days)

For patients who are unable to return to the clinical site for the *6- and 12-month* assessments because of extreme geographic distance, the clinical coordinator will obtain the required data from a remote clinical site outside of the CTSN sites. The remote clinical site *must* be identified in advance of discharge from the index hospitalization. All efforts must be made to acquire all follow-up at the CTSN clinical site. *All 24-month (Primary Endpoint) assessments must be performed in accordance with the protocol defined data collection whether the visit is conducted at a CTSN clinical site or remotely.* The 36, 48 and 60 month vital status checks may be conducted via telephone or via a search of medical records.

Surgical Procedures

Initial surgical intervention and event driven

The initial surgical procedure (MV surgery \pm TV repair) will be reported on the initial surgical Procedure form and all subsequent operations must be reported on the follow up surgical procedure form within 48 hours of the knowledge of the event. If the operation is to address a complication, the coordinator must also complete an AE report.

Initial Surgical Procedure

Routine information will be collected on the standard surgical procedure, the MV procedure, TV procedure and any concomitant procedures.

Follow-up Surgical Procedure

Information about any surgical procedure(s) performed following the initial surgical procedure and during the follow-up period through 24 months post-randomization will be collected on this form.

Hospitalizations

Index hospitalization

For all patients, the index (baseline) hospitalization must be reported on the Hospitalization form. This form collects limited information about LOS, days in ICU, and disposition at time of discharge (home, skilled nursing facility, rehabilitation facility, death).

Medications

At 30 days (-7 days, +35 days), 6 (± 30 days), 12 (± 30 days), and 24 months (± 60 days) post randomization and event driven

All cardiovascular medications will be recorded at each study visit, and also as indicated at the time of associated AEs.

Physical Examination

At 30 days (-7 days, +35 days), 6 (± 30 days), 12 (± 30 days), and 24 months (± 60 days) post randomization

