Reoperation for TR: The difference in the rate of requiring subsequent TV annuloplasty after the initial MVS will be compared between randomization groups. Reoperation for TR may not occur because death from any cause precedes the event; thus, it is possible that censoring patients at all-cause mortality will lead to biased estimates when analyzing time to first event. Therefore, competing risks analysis using the methods of Fine and Gray (1999) will be used to estimate group differences.

Degree of TR: Between group differences in the presence of severe TR at two years post randomization or, for patients enrolled with less than moderate TR, the progression by two grades will be compared using a two-tailed 0.05 level chi-squared test of the equality of two proportions.

MACCE: The proportion of patients experiencing major adverse cerebrovascular and cardiac events, defined as the composite event of death, stroke, and the serious heart failure events, is of particular interest. Given that this trial's primary endpoint is likely to be determined by echocardiographic assessments, it will be important to supplement the finding of a treatment effect (or lack of one) for the primary endpoint with a corresponding effect on a more clinical endpoint such as MACCE (and its component elements). As the trial is not powered to detect a difference in MACCE, a statistically significant treatment difference in MACCE is not expected; however, an observed difference in MACCE, consistent in direction with that observed for the primary endpoint will serve to validate the trial's findings. No matter the result, the interpretation of the trial's results will necessarily consider the difference in MACCE observed between treatment groups. The rate of major cerebrovascular or cardiac events will be compared between randomization groups over 24 months post-randomization using a Cox proportional hazards regression model. We expect MACCE two-year event rates to be approximately 15% for patients randomized to MVS alone. With a total of 400 patients randomized with equal allocation to MVS alone or to TR repair plus MVS, there is 90% power to detect an absolute decrease in MACCE to approximately 9-10% for patients randomized to TR plus MVS compared to MV surgery alone.

A number of additional secondary analyses are planned to supplement the primary analysis and aid interpretation of the trial's results.

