5.2.1 Clinical and Functional Outcomes

- A composite of major adverse cardiac and cerebrovascular events (MACCE), including stroke, death, and serious heart failure events by 24 months post-randomization
- Re-operation for TR by 24 months post-randomization
- NYHA classification at 30 days, 6, 12 and 24 months post-randomization.
- Diuretic Use at 30 days, 6, 12 and 24 months
- 6MWT at 30 days, 6, 12 and 24 months post-randomization.
- Gait Speed Test for Frailty at 12 and 24 months post-randomization.

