6.5.1 Analysis of the Primary Outcome and Determination of Sample Size

The primary outcome is treatment failure defined as the composite of (1) death from any cause, (2) reoperation for TR, (3) presence of severe TR at two years post randomization or, for patients enrolled with less than moderate TR and annular dilatation, progression by two grades (i.e., from none/trace TR to moderate TR) at two years. The null hypothesis is that there is no difference in the probability of treatment failures at two years post randomization between patients randomized to undergo TV repair during MVS compared to patients randomized to undergo MVS alone. The primary null hypothesis will be tested in an intent-to-treat analysis using a 0.05 level two-tailed normal approximation (Wald) test.

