6.5.2 Analyses of Secondary Clinical Endpoints

6.5.2.1 Clinical and Functional Outcomes

MACCE: The rate of major cerebrovascular or cardiac events (defined as the

composite event of death, stroke, and serious heart failure events) will be compared between randomization groups over 24 months post-randomization using a Cox proportional hazards regression model.

Reoperation for TR: The difference in the rate of requiring subsequent TV annuloplasty after the initial MVS will be compared between randomization groups over 24 months post-randomization. Reoperation for TR may not occur because death from any cause precedes the event; thus, it is possible that censoring patients at all-cause mortality will lead to biased estimates when analyzing time to first event. Therefore, competing risks analysis using the methods of Fine and Gray (Fine & Gray, 1999) will be used to estimate group differences.

NYHA: The distribution of NYHA at 30 days, 6, 12 and 24 months will be presented for each randomization arm and compared using chi-squared tests.

Diuretic Use: The distribution of diuretic use at 30 days, 6, 12 and 24 months will be presented for each randomization arm and compared using chi-squared tests.

Six Minute Walk: Differences between groups in the distances travelled during the 6MWT at 30 days, 6, 12 and 24 months will be compared using Wilcoxon Rank-Sum tests.

Gait Speed Tests: Differences between groups in gait speed at 12 and 24 months will be compared using Wilcoxon Rank-Sum tests.

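### The reoperation-for-TR analysis counts only a subsequent annuloplasty, which is narrower than the listed endpoint and than the reoperation component of the primary composite

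*SAP*

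**What the plan says.** The event being compared is stated once in each document, in nearly identical text.

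- SAP 6.5.2.1, Reoperation for TR: "The difference in the rate of requiring subsequent TV annuloplasty after the initial MVS will be compared between randomization groups".
- Protocol, Analyses of Secondary Endpoints, Reoperation for TR: "The difference in the rate of requiring subsequent TV annuloplasty after the initial MVS". The protocol places this under its heading for the individual components of the primary endpoint.
- The method follows in the same SAP paragraph: "competing risks analysis using the methods of Fine and Gray (Fine & Gray, 1999) will be used to estimate group differences". Death from any cause is the only competing event named.

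Elsewhere the event carries no restriction on procedure.

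- SAP 5.2.1 lists the secondary endpoint as "Re-operation for TR by 24 months post-randomization".
- SAP 6.5.1 defines treatment failure as the "composite of (1) death from any cause, (2) reoperation for TR" and TR status at two years. The protocol defines it the same way.
- SAP 6.5.2.6 compares TR re-operation by 30 days after surgery, again without naming a procedure.

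On data, the protocol section on readmission and reoperations says "All re-operations and re-operation for TR in particular will be recorded through 24 months". The follow-up surgical procedure form collects "Information about any surgical procedure(s) performed following the initial surgical procedure and during the follow-up period through 24 months post-randomization".

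**The concern.** An annuloplasty is one kind of tricuspid operation. The sentence that tells a programmer what to count names only that kind, although its heading, the endpoint list and the primary composite all refer to reoperation for TR in general. No section lists which procedures make up a reoperation for TR, so nothing else in the documents explicitly overrides the narrow phrase.

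At stake is whether this analysis can explain the composite. The protocol expects the primary endpoint to be determined largely by echocardiography and wants clinical outcomes to be read beside it. Reoperation is one of the two non-echocardiographic components. If it is counted on a narrower rule than the composite uses, a reader cannot split the treatment failures into their parts.

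The two arms also differ in their starting point. In the protocol's section on tricuspid valve surgery, "Patients randomly assigned to receive TV repair in addition to MVS will undergo concomitant TV repair", and that repair is an annuloplasty ring. Patients assigned to mitral surgery alone have no ring unless they cross over. A rule that counts only annuloplasties may therefore capture a different fraction of reoperations in each arm.

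**Working it through.** **The plan's own figure.** There is none to reproduce. Neither document states a reoperation rate, an expected count or a power for reoperation. The trial's sizing (25% against 12%, 400 patients) concerns the composite and uses no reoperation rate, so it does not depend on this wording.

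**Step 1: one patient traced through both rules.** Take a patient who has a tricuspid replacement for TR before 24 months, is alive at 24 months, and does not meet the echocardiographic criteria there.

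- Primary analysis (SAP 6.5.1 and 6.5.1.2): treatment failure, through component (2).
- Reoperation analysis (SAP 6.5.2.1, read literally): no subsequent annuloplasty, so no event. The replacement is not a competing event either, since only death is named. The patient stays in the risk set as event-free.

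The same holds for a ring revision or removal and for a repair without a ring. Each such patient is a failure in the composite that this component analysis does not show.

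**Step 2: how far the comparison could move.** The inputs from the documents are 400 patients allocated 1:1, so 200 per arm. Everything else is assumed: a true risk r of reoperation for TR, equal in both arms, and the share s of those reoperations that are annuloplasties.

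Counted events per arm = 200 × r × s.

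Counted ratio (repair to control) = (200 × r × s_repair) / (200 × r × s_control) = s_repair / s_control.

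With r = 2% there are 200 × 0.02 = 4 true events per arm, and the true ratio is 4/4 = 1.0.

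| Assumed share, repair | Assumed share, control | Counted events, repair v control | Counted ratio |
|---|---|---|---|
| 25% | 100% | 1 v 4 | 0.25 |
| 50% | 75% | 2 v 3 | 0.67 |
| 75% | 75% | 3 v 3 | 1.0 |
| 75% | 50% | 3 v 2 | 1.5 |

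Changing r from 1% to 4% moves the true count from 200 × 0.01 = 2 to 200 × 0.04 = 8 per arm and leaves the ratios unchanged. These are ratios of expected counts, not Fine and Gray estimates. They show only that the counted ratio depends on two shares that the documents do not give. At counts this small, chance variation would also be large.

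**The case against.** The strongest reply is that this is loose drafting in one phrase. The heading says Reoperation for TR. The next sentence, which motivates the competing-risks model, names the event as reoperation for TR. The protocol presents the analysis as a component of the primary endpoint, and that component is unrestricted. All reoperations are recorded, so no information is lost. On this view the sponsor meant any reoperation for TR and would have programmed it so.

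Much of this stands. The intention was probably the wider event, and nothing shows a decision to exclude replacements. But the phrase is the only statement of what is compared, it stands in both documents, and it conflicts with the endpoint. The protocol has readmissions, including those for a TR operation, classified and adjudicated, but that does not say which procedures count. Probable intent is a reason to expect easy agreement on the correction, not a reason to leave the rule.

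A reader might go further and infer that the omission falls mainly on the repair arm and so favours repair, because a patient with a ring seems less likely to receive a second annuloplasty. The ring makes a difference between arms possible, but the documents do not say which operations are expected at reoperation in either arm, and control patients could also have a replacement. As the table shows, the distortion can go either way or vanish. A reader might also infer that the primary composite is narrowed. Its text is not: both documents give reoperation for TR without restriction there.

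**Conclusion.** Wrong as written, within a limited scope. The event rule in SAP 6.5.2.1 and in the matching protocol paragraph is narrower than the endpoint it is meant to analyse and than component (2) of the primary composite. Taken literally, it makes the component analysis irreconcilable with the composite whenever a reoperation for TR is anything other than an annuloplasty.

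The conclusion about the wording rests on the texts alone. The effect on the estimate cannot be sized from the documents. The range of 0.25 to 1.5 reflects assumed annuloplasty shares under equal true risk; it is neither a forecast nor a bound. Only this secondary analysis is affected.

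**What to change.** In both documents, replace the phrase about requiring a subsequent TV annuloplasty with reoperation for TR of any procedure type, and state that this is the same event as component (2) of the primary endpoint. List the procedure types that count: annuloplasty, other repair, ring revision or removal, and replacement. Keep the Fine and Gray analysis with death as the competing event, and add a table of procedure type at reoperation by arm.

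The cost is one phrase in each document and one descriptive table. No new data are needed, because the follow-up surgical procedure form already covers every operation through 24 months. The SAP's statement of purpose allows revisions before data lock, so the change should be made by then.
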